The Impact of the Attention Training Technique on Attention Control and High Worry

Study Protocol and Statistical Analysis Plan

NCT03216382

June 10, 2021

Study Protocol and Statistical Analysis Plan

NCT03216382

Protocol

- Phone screen to assess eligibility
- Visit 1: Baseline
 - Participants completed consent form, a demographic questionnaire, the GAD-Q-IV, MCQ-30, ACS, PSWQ-PW, SMQ, and the CESD-R.
 - Participants completed the dot-probe task, ANT, and breathing focus task.
 - Participants assigned to complete daily diary every evening, monitoring worry and attention.
- Week 1: Diary
 - Monitoring worry and attention at home every evening
- Visit 2: Preintervention (1 week after baseline)
 - Participants completed the MCQ-30, the ACS, the SMQ, and the PSWQ-PW.
 - Participants completed the dot-probe, ANT, and breathing focus task.
 - Participants randomly assigned to one of the two conditions: attention training or control.
 - Participants completed self-focused attention rating scale.

- Participants given rationale (same for both conditions).
- Participants listened to ATT or control recording.
- Participants recomplete the self-focused attention rating scale and the credibility and expectancy questionnaire.
- Participants asked to listen to assigned recording once per day over the follow week while continuing to monitor worry and attention.
- Week 2: Recording and Diary
 - Participants listened to assigned recording once per day and complete diary every evening.
 - Before and after recording, participants completed self-focused attention rating scale. Participants also asked at the end of listening to the recording to what percentage they focused on the recording.
- Visit 3: Postintervention (1 week after preintervention)
 - Participants completed the MCQ-30, the ACS, and the PSWQ-PW.
 - Participants completed the dot-probe, the ANT, and the breathing focus task.
 - Participants were debriefed about the goals and hypotheses of the study.
 - Those in the control condition were offered the opportunity to listen to the ATT recording in the lab.

Data Analysis Plan

Scores from the questionnaires, the ANT, dot-probe task, and breathing focus task were analyzed using a 3x2 repeated measures Oneway Analysis of Variance (ANOVA), with time as a

variable with three levels (visits 1, 2 and 3) and condition as a variable with two levels (ATT and Control). This was a pre-planned analysis.

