Diary data were analyzed using hierarchical linear modelling. The proposed structure of the data included 2 levels, the first level representing the data across time points (i.e., an individual's responses over the course of the study), and the second level representing the participant's assigned condition (ATT vs. Control). A piecewise analysis of the data was conducted with a random intercept and fixed slopes. Linear multilevel models were run separately for each outcome variable. Predictor variables included condition, time (piece 1: baseline, or visit 1 to visit 2 and piece 2: intervention period, or visit 2 to visit 3), and an interaction between condition and time. Quadratic models were also run, in case change was not linear. This was a pre-planned analysis.

Only uncontrollability of worry and self-focused attention were analyzed. It was decided post-hoc that uncontrollability and intensity may be redundant, and thus uncontrollability was chosen due to perceived uncontrollability of worry being part of the diagnostic criteria of GAD. Further, minutes of worry and frequency of worry episodes were difficult to interpret, as there was huge variability in responses. Many participants reported that they found it very difficult to quantify their worry in this way and they were not confident in their responses.

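### The visit-score ANOVA enters two pre-randomisation visits as outcome levels; a baseline-adjusted Visit 3 comparison would usually be more powerful and would give a treatment estimate

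*Combined protocol and SAP*

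**What the plan says.** According to the Data Analysis Plan, all questionnaire and task scores "were analyzed using a 3x2 repeated measures Oneway Analysis of Variance (ANOVA"). Of its two factors, time is the "variable with three levels (visits 1, 2 and 3) and condition as a variable with two levels (ATT and Control"). The plan describes this analysis as planned in advance.

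The Protocol section sets the order of events:

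- "Visit 1: Baseline": first set of scores.
- Visit 2, labelled preintervention: "Participants completed the MCQ-30, the ACS, the SMQ, and the PSWQ-PW", then the three tasks, and only after these "Participants randomly assigned to one of the two conditions: attention training or control".
- Visit 3, postintervention: the MCQ-30, ACS and PSWQ-PW again, and "Participants completed the dot-probe, the ANT, and the breathing focus task".

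Six instruments are therefore scheduled at all three visits: MCQ-30, ACS, PSWQ-PW, dot-probe, ANT and breathing focus task. The SMQ is not listed at Visit 3, and the GAD-Q-IV and CESD-R appear only at Visit 1.

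For the visit scores the plan names no sphericity check or correction, no contrast, no baseline-adjusted estimate and no confidence interval. The diary model does separate the two periods, with "time (piece 1: baseline, or visit 1 to visit 2 and piece 2: intervention period, or visit 2 to visit 3"). The diary analysis is not part of this point.

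**The concern.** The ANOVA treats the three visits as levels of equal standing, although two of them precede randomisation. Read as the time-by-condition interaction, the test has 2 degrees of freedom. One of them compares the arms on the change from Visit 1 to Visit 2, where no treatment effect is possible. Three things are at stake.

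- **Efficiency.** The two baselines could serve as covariates for Visit 3. The ANOVA does not use them in that way.
- **Estimate.** An F test on 2 df gives neither the size nor the direction of the Visit 3 difference, and no interval.
- **Type I error.** Without a correction, the repeated measures F test holds 5% only under sphericity. That is doubtful when two visits are baselines and the third follows an intervention.

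**Working it through.** **Inputs.** From the documents: two arms, three visits, randomisation after the Visit 2 scores. The documents give no sample size, alpha, effect size, SD or correlation, so there is no stated figure to reproduce. Assumed: two-sided alpha 0.05, SD 1 at each visit, n = 30 per arm, effect d = 0.5 SD, and several correlation patterns.

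**Step 1: where an effect can appear.** Randomisation makes the expected arm differences (0, 0, d) at Visits 1, 2 and 3. That the Visit 2 scores precede randomisation rests on the bullet order and the visit label, which agree.

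**Step 2: the interaction, under compound symmetry with correlation ρ.** The mean of (0, 0, d) is d/3. The squared deviations sum to (d/3)² + (d/3)² + (2d/3)² = 2d²/3. The noncentrality is (n/2)(2d²/3)/(1−ρ) = nd²/[3(1−ρ)], on 2 and 2(2n−2) = 116 df.

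**Step 3: a 1-df contrast, Visit 3 minus the mean of Visits 1 and 2.** Its variance is 1 + (1+ρ)/2 − 2ρ = 1.5(1−ρ). The noncentrality is the same nd²/[3(1−ρ)], but on 1 and 2n−2 = 58 df. Comparing it with Step 2 isolates the cost of the extra df.

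**Step 4: ANCOVA of Visit 3 on condition, Visit 1 and Visit 2.** The residual variance is 1 − 2ρ²/(1+ρ). The noncentrality is nd²/{2[1 − 2ρ²/(1+ρ)]}, on 1 and 2n−4 = 56 df. It is divided by 1+T for chance baseline imbalance and averaged over T = [2/(2n−3)]F(2, 2n−3).

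With nd² = 30 × 0.25 = 7.5:

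| ρ | Noncentrality, interaction and contrast | Noncentrality, ANCOVA (before 1+T) | Power, interaction | Power, contrast | Power, ANCOVA |
|---|---|---|---|---|---|
| 0.5 | 7.5/1.5 = 5.00 | 7.5/1.333 = 5.63 | 49% | 59% | 63% |
| 0.7 | 7.5/0.9 = 8.33 | 7.5/0.847 = 8.85 | 72% | 81% | 82% |
| 0.8 | 7.5/0.6 = 12.50 | 7.5/0.578 = 12.98 | 89% | 94% | 94% |
| 0.9 | 7.5/0.3 = 25.00 | 7.5/0.295 = 25.45 | 99.6% | 99.8% | 99.8% |

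Other assumed settings, interaction vs ANCOVA:

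- d = 0.3, 30 per arm: 20 vs 28% at ρ = 0.5, 31 vs 41% at 0.7, 45 vs 55% at 0.8, 76 vs 83% at 0.9.
- d = 0.8, 30 per arm: 90 vs 96% at ρ = 0.5, 98.8 vs 99.6% at 0.7, no practical difference above that.
- d = 0.5, ρ = 0.5: 34 vs 45% with 20 per arm, 73 vs 85% with 50 per arm.

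**Step 5: other correlation patterns, by simulation** (d = 0.5, 30 per arm; ranges span repeat simulations). The interaction is Greenhouse-Geisser corrected.

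| Pattern | Interaction | Contrast | ANCOVA |
|---|---|---|---|
| AR(1), ρ = 0.7 | 57–58% | 65% | about 75% |
| Baselines 0.9, pre-post 0.5 | 49–50% | about 50% | 58–59% |
| Baselines 0.9, pre-post 0.7 | 72% | 73% | about 77% |

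The source of the gain changes. Under compound symmetry it is mostly the saved df. When the baselines correlate 0.9 with each other, interaction and contrast are nearly level and the gain comes from covariate adjustment. Under AR(1) both contribute.

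**Step 6: type I error of the interaction, 30 per arm, by simulation.**

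| Pattern | Uncorrected | Greenhouse-Geisser |
|---|---|---|
| Compound symmetry | about 5% | about 5% |
| AR(1), ρ 0.5–0.9 | 5.2–5.7% | about 5% |
| Baselines 0.8–0.9, pre-post 0.5–0.7 | 6–7% | about 5% |

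The ANCOVA stays at 4.8–5.2% throughout.

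**The case against.** The strongest reply is that the planned test is sound. Before randomisation the expected arm differences are zero, so the interaction null is false only if the arms differ at Visit 3. With sphericity handled, rejection is a valid 5% test of treatment. This stands. A reader might infer that a significant interaction fails to show a post-intervention difference, since it could be driven by the two baselines. Randomisation does not allow that reading: an interaction driven by baseline imbalance is a chance false positive, already counted in the 5%. What is missing is the estimate.

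A reader might also take the condition main effect as the treatment test. It would average d over three visits to d/3 and, at d = 0.5 with 30 per arm under compound symmetry, have only 10–12% power. The plan does not say which effect it uses, and the label Oneway sits badly with 3x2. But nothing in the documents adopts the main effect, and a 3x2 repeated measures design is ordinarily read through its interaction. One clarifying sentence settles it; those figures carry no weight here.

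Third, every magnitude is hypothetical, and the largest power loss and the largest type I error come from different correlation patterns. This also stands: they should not be added together.

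Finally, the analysis is reported as done, so nothing added now can replace it. True, and the remedy is limited accordingly.

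**Conclusion.** The point holds as a low-cost improvement in efficiency and reporting, not as a finding of bias. The omissions are plain in the text; their effect in this trial is unknown, because sample size, effect and correlations are all assumed.

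At d = 0.5 and 30 per arm, the baseline-adjusted comparison gains about 10–14 points of power under compound symmetry with ρ of 0.5–0.7. It gains about 17 points under AR(1) at 0.7, and about 4–9 points when the baselines correlate 0.9 with each other. The gain is small at high correlation under compound symmetry or with large effects. A reader might put all of it down to the df spent on the two baselines; the unequal-correlation cases show that this is not general. Uncorrected type I error is about 5–7% over the patterns examined, and Greenhouse-Geisser removes the excess.

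**What to change.** 1. Keep and report the pre-planned ANOVA. State that the time-by-condition interaction is its treatment test, and apply Greenhouse-Geisser.
2. For each score from the six instruments measured at all three visits, add an ANCOVA of Visit 3 on condition, Visit 1 and Visit 2. Report the adjusted difference with its 95% CI.
3. If visits are missing, an equivalent mixed model with the arms constrained equal at Visits 1 and 2 and a small-sample correction is an option. The documents do not mention missing data, so they give no ground for requiring it.
4. Label the adjusted estimates as added after the original plan and supplementary. If an estimate and its ANOVA disagree, report both; the ANOVA remains the pre-planned test.

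Cost: one short model per score on data already collected, a standard correction and a few sentences, with no new participants or measurements. The downside is a little extra analysis, whose estimates cannot replace the pre-planned test.

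### The diary model has a random intercept only. If model-based SEs were used, the SE of condition × piece 2 is usually too small when week-2 slopes vary between participants, and too small under positive serial correlation. The size is unknown.

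*Combined protocol and SAP*

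**What the plan says.** The Data Analysis Plan describes a two-level model for the evening diary entries: "The proposed structure of the data included 2 levels, the first level representing the data across time points". The covariance statement is one sentence: "A piecewise analysis of the data was conducted with a random intercept and fixed slopes". The main predictors are listed thus: "Predictor variables included condition, time (piece 1: baseline, or visit 1 to visit 2 and piece 2: intervention period, or visit 2 to visit 3". The list closes with the term that should carry the treatment effect, worded only as "and an interaction between condition and time". It adds "Linear multilevel models were run separately for each outcome variable" and "Quadratic models were also run, in case change was not linear". Two diary outcomes were analysed: uncontrollability of worry and self-focused attention.

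The Protocol places allocation at visit 2: "Participants randomly assigned to one of the two conditions: attention training or control". The recording is then used through week 2: "Participants listened to assigned recording once per day and complete diary every evening". So piece 1 lies before randomisation and piece 2 after it.

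The plan does not say which condition × time term is the treatment contrast, how the two pieces or the quadratic terms were coded, what residual structure was used, or whether the SEs were model-based or robust. It gives no sample size, variance component or diary SE.

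**The concern.** A random intercept alone implies that any two entries from one person are equally correlated, however far apart in time. Two things break that. People may change at different rates during week 2, or neighbouring evenings may resemble each other more than distant ones. Either way, a model-based SE treats person-level differences in change as independent daily noise.

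The term affected is condition × piece 2, which carries the diary treatment effect. With complete data its point estimate stays unbiased; what suffers is the confidence interval and the p-value. A result just under 0.05 might not survive a correct SE. Both features are plausible for daily ratings of worry, but the documents do not show that either occurred. The visit-based ANOVA is not affected by this point.

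**Working it through.** The plan reports no figure that could be reproduced, so the check compares the SE that a random-intercept model would report with the true SE.

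**Inputs from the documents.** Daily evening entries; one week from visit 1 to visit 2 and one week from visit 2 to visit 3; individual randomisation to two conditions; random intercept, no random slopes.

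**Assumptions, not in the documents.** 14 complete entries on days −6 to 7 with the knot at day 0; residual SD 1; 1:1 allocation, 30 per arm; model-based SEs; nominal two-sided 5%. Slope SDs are in residual SDs per day, so 0.10 per day is 0.7 residual SDs over 7 days.

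**Formulas.** Let X hold one person's intercept and time terms, and A = (X'X)⁻¹X'. With balanced data the estimate is the difference between arms in mean per-person least-squares slopes.

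- True variance ∝ the piece-2 element of A V A', where V is the AR(1) matrix plus the slope-variance terms.
- Model variance ∝ s² × c, where c is the piece-2 element of (X'X)⁻¹ and s² is the expected pooled within-person residual variance.
- Ratio r = true SE / model SE. Type I error = 2(1 − Φ(1.96/r)).

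**Separate slopes for the two pieces** (c = 0.01840):

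- Neither feature: r = 1.00, 5.0%.
- Piece-2 slope SD 0.05: true 0.01840 + 0.0025 = 0.02090; model 1.0157 × 0.01840 = 0.01869; r = √(0.02090/0.01869) = 1.058; 6.4%.
- Piece-2 slope SD 0.10: true 0.02840; model 1.0628 × 0.01840 = 0.01955; r = 1.205; 10.4%.
- AR(1) 0.3: true 0.02822; model 0.9377 × 0.01840 = 0.01725; r = 1.279; 12.5%.
- Slope SDs of 0.02 and 0.03 give 5.2% and 5.5%. AR(1) of 0.1 and 0.2 gives 7.1% and 9.6%.

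**Dependence on time coding** (type I error of the week-2 term):

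| Coding | c | Slope SD 0.05 | Slope SD 0.10 | AR(1) 0.3 |
|---|---|---|---|---|
| Separate slopes | 0.0184 | 6.4% | 10.4% | 12.5% |
| Change in slope at visit 2 | 0.0703 | 5.2% | 5.9% | 12.1% |
| Separate slopes plus level shift at visit 2 | 0.0357 | 5.6% | 7.4% | 10.4% |

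The coding moves the slope-variance result a good deal and the serial-correlation result much less.

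**Cases that run the other way** (separate-slope coding):

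- AR(1) −0.2: r = 0.845, 2.0%.
- Piece-1 slopes only, SD 0.20: r = 0.921, 3.3%.
- Piece-1 SD 0.20 with piece-2 SD 0.05, uncorrelated: true 0.02090; model 1.1936 × 0.01840 = 0.02196; r = 0.976; 4.5%.

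The two piece-1 cases do not carry over to change-in-slope coding, because that contrast contains the piece-1 slope. The last case then has true variance 0.07035 + 0.0025 + 0.04 = 0.11285 against 1.1936 × 0.07035 = 0.08397, so r = 1.159 and 9.1%.

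**Separate quadratics in each piece, piece-2 slope SD 0.10.** Slope at the knot: r = 0.987, 4.7%. Slope at day 4: r = 1.123, 8.1%. Change from the knot to day 7: r = 1.169, 9.4%.

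**What this does to a p-value** (linear model, separate slopes). The correct interval is wider by 6% or 21% at slope SD 0.05 or 0.10, and by 28% at AR(1) 0.3. From 2(1 − Φ(1.96 r)), a reported p-value must be below about 0.038, 0.018 and 0.012 respectively to stay significant at 5%.

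**Simulation check.** With 10,000 runs per setting (Monte Carlo SE about 0.2 to 0.3 points), the linear random-intercept model at 15 and 30 per arm rejected in 9.8% and 10.8% at slope SD 0.10, and in 12.7% and 12.9% at AR(1) 0.3. Comparing per-person slopes, which equals CR2 in balanced data, held 4.6% to 5.3% across all 32 settings. With 15% of entries missing at random (3,000 runs, Monte Carlo SE about 0.4 points), CR2 with participant-based df held 4.3% to 5.3%.

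**The case against.** The best reply is that no defect has been shown. Every percentage above comes from assumed inputs, the range runs from 2.0% to 12.5%, and nothing in the documents places this trial within it or shows that a diary result was close to 0.05. That stands, and it is why the size must be called unknown.

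Three narrower objections also stand.

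- It is not true that slope variation in piece 2 always shrinks the SE. With separate slopes, much larger piece-1 variation reverses the direction.
- A threshold such as a slope SD of 0.05 depends on a coding that the plan does not fix. Its wording favours separate slopes but does not settle the matter.
- The serial-correlation half rests on silence. Only the absence of random slopes is stated. If AR(1) residuals were fitted, that half falls away; if participant-level robust SEs were used, the whole point does.

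It might also be said that the quadratic models give protection. They do so only for the slope on the knot day. Slope variation still shrinks the SE of the mid-week slope and of the week-2 change, and the plan does not say how the quadratic was built or centred.

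Finally, this was a parsimonious pre-planned model and only two diary outcomes are involved. That limits the reach of the point, but not the case for a cheap check.

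**Conclusion.** The point holds in conditional form. The plan sets slope variance to zero and leaves the residual structure and SE type unstated. With model-based SEs, the SE of condition × piece 2 is usually too small if piece-2 slopes vary, and too small if positive serial correlation remains. Under the stated assumptions the error rate is near nominal at slope SDs of 0.02 to 0.03, between 5.9% and 10.4% at 0.10 depending on coding, and between 10.4% and 12.5% at AR(1) 0.3.

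A reader might infer that the reported diary p-values are wrong, or that the analysts assumed independent residuals. The documents support neither: they give no variance components, residual correlation, SE type or diary p-values. What can be said is that a diary p-value between roughly 0.01 and 0.05 cannot be relied on until those facts are reported. The plan should be supplemented on this point; confidence is medium.

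**What to change.** - Name condition × piece 2 as the diary treatment contrast, and state the time coding and the SE type actually used.
- Report that contrast, and for the quadratic model the week-2 change, with participant-level cluster-robust SEs and a small-sample correction (for example CR2 with participant-based df). Alternatively, compare per-person piece-2 slopes between conditions.
- Show this beside the pre-planned random-intercept result and label it post hoc.
- Report the piece-2 slope variance and the residual lag-1 correlation, so that readers can see whether the issue arises.
- Optionally, fit a random piece-2 slope with AR(1) residuals as a further check.

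The cost is a re-analysis of existing data and a few lines of text. If neither feature is present, the interval widens only because df are counted in participants. At 15 per arm the multiplier is 2.048 on 28 df against about 1.966 (ratio 1.042, about 4%). At 30 per arm it is 2.002 on 58 df against about 1.963 (ratio 1.020, about 2%). The optional model may need some convergence work.

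### One of four named diary worry items was analysed, the choice over intensity was post-hoc, and the plan does not say whether results by condition were known

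*Combined protocol and SAP*

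**What the plan says.** The Protocol section describes the diary only in general terms (Week 1: "Monitoring worry and attention at home every evening") and lists no items. The items appear in the last paragraph of the Data Analysis Plan, which names uncontrollability, intensity, minutes of worry and frequency of worry episodes. That paragraph begins "Only uncontrollability of worry and self-focused attention were analyzed". Self-focused attention is an attention item, so one of the four named worry items was analysed.

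Two separate reasons are given:

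- **Intensity:** "It was decided post-hoc that uncontrollability and intensity may be redundant". Uncontrollability was kept because it forms part of the diagnostic criteria for GAD.
- **Minutes and frequency:** "minutes of worry and frequency of worry episodes were difficult to interpret, as there was huge variability in responses", and "Many participants reported that they found it very difficult to quantify their worry in this way". No date or stage is given for this decision.

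The paragraph before it describes the piecewise multilevel model. It says "Linear multilevel models were run separately for each outcome variable" and closes with "Quadratic models were also run, in case change was not linear. This was a pre-planned analysis".

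**The concern.** When several items measure the same construct and one is kept after data collection, what matters for bias is whether the person choosing could see results by condition. The word post-hoc does not answer that. For minutes and frequency, the stated reason (wide variability) means that at least some responses had been looked at, but not when or by whom.

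The redundancy of intensity is put forward as a possibility, with no correlation or other evidence. A reader therefore cannot tell whether intensity showed a condition-by-time effect like that of uncontrollability. What is at stake is how far the diary worry result can be trusted. The questionnaire, ANT, dot-probe and breathing focus analyses do not depend on this choice.

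**Working it through.** **Step 1. Count.** Named diary worry items: 4. Analysed: 1 (uncontrollability). Not analysed: 4 − 1 = 3 (intensity, minutes, frequency).

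**Step 2. What is known about timing.**

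- Intensity: expressly post-hoc. Whether results by condition were visible is not stated.
- Minutes and frequency: after some responses were seen, stage not stated. Week 1 diaries came before Visit 2, where the Protocol places "Participants randomly assigned to one of the two conditions: attention training or control". A decision made on Week 1 diaries alone could not have been influenced by results by condition. The text neither confirms nor excludes this.

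**Step 3. What a choice by result would cost.** The documents give no alpha, sample size or item correlation, so there is no plan figure to reproduce. Assumed inputs: two-sided alpha 0.05 (critical value 1.96), one correctly specified test per item, no true effect, and a correlation r between the test statistics for uncontrollability and intensity.

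Formula: P(at least one significant) = 1 − P(|Z1| ≤ 1.96 and |Z2| ≤ 1.96), with Z1 and Z2 standard normal and correlation r.

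| r | P(at least one) |
|---|---|
| 0 | 1 − 0.95² = 0.0975 |
| 0.5 | 0.0907 |
| 0.7 | 0.0835 |
| 0.9 | 0.0704 |

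A simulation of 2,000,000 draws gave 0.0975, 0.0909, 0.0834 and 0.0704. If the choice was blind to condition, the figure is 0.05 at every r. The 5% is a reference value and not this plan's own error rate, because the plan runs both linear and quadratic models over two time pieces.

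**Step 4. Would seeing intensity tell the reader anything?** Let p be the chance that a single item is significant. Given that uncontrollability is significant, the chance that intensity is not is (P(at least one) − p) / p.

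| r | No true effect, p = 0.05 | True effect, assumed 50% power for each item, p = 0.50 | Ratio |
|---|---|---|---|
| 0.9 | (0.0704 − 0.05)/0.05 = 0.407 (from unrounded values) | (0.572 − 0.500)/0.500 = 0.144 | 2.8 |
| 0.7 | (0.0835 − 0.05)/0.05 = 0.669 (from unrounded values) | (0.627 − 0.500)/0.500 = 0.253 (from unrounded values) | 2.6 |
| 0.5 | (0.0907 − 0.05)/0.05 = 0.815 (from unrounded values) | (0.667 − 0.500)/0.500 = 0.333 (from unrounded values) | 2.4 |

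Disagreement between the two items is thus about 2.4 to 2.8 times as likely when there is no effect as when there is one at 50% power. Intensity is informative, but modestly so. Significance is used here only to measure that. The comparison proposed below rests on estimates and intervals.

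**The case against.** The strongest reply is that the document already deals with most of this. It says what was analysed, labels the choice over intensity post-hoc, and gives reasons that do not refer to the treatment effect: a diagnostic criterion, wide variability and participants' lack of confidence. This stands. What remains open is the timing relative to results by condition, and the redundancy that is asserted but not shown.

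A reader might go further in four ways that the documents do not support:

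- **That the pre-planned label contradicts the post-hoc choice.** It does not. The label closes the paragraph on the model, and the item choice is described separately in the next paragraph.
- **That the dropped items went unreported.** The document says only that they were not analysed. It contains no results, so nothing can be said about descriptive data given elsewhere.
- **That the best of four items was picked.** On the assumptions in Step 3, that would give 9.4% to 18.5% (correlation 0.9 to 0). Nothing in the text suggests a free choice among four, and minutes and frequency have their own stated reasons, so this range should not be used to size the problem.
- **That the item was chosen by result.** The text is silent on this, and silence is not evidence.

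It is also fair to say that, if the two items really are near-redundant, the high-correlation end of the table applies (about 7.0% at 0.9). Nor can any later analysis restore pre-specification to a study written up in the past tense.

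**Conclusion.** The point holds as a limited one. One of four named diary worry items was analysed, the choice over intensity was post-hoc on an undemonstrated ground, and the document does not say whether results by condition were known. The risk of selective-outcome bias in the diary worry result is possible and not shown.

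On the assumed inputs, a choice between two items by result would cost about 2 percentage points at correlation 0.9 (7.0% against 5%) and about 4 at 0.5 (9.1% against 5%). The cost is zero if the choice was blind to condition. Confidence is high about what the text leaves unsaid, and does not extend to any claim that bias occurred. The document names no primary outcome, so nothing shows that the trial's conclusion rests on this item. The weight is minor to moderate. It is worth fixing because the data already exist and the comparison directly tests the asserted redundancy.

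**What to change.** 1. Keep uncontrollability as the analysed worry item. Run the same piecewise multilevel model on intensity, and report its condition-by-time estimate for the intervention piece, with a 95% CI, beside the one for uncontrollability. Label the comparison post hoc and descriptive, with no significance claim.
2. If the two response scales differ, also give each estimate divided by the between-person standard deviation of participants' Week 1 means for that item. Defining it this way matters because the diary has repeated daily responses.
3. State the timing. Possible text: *Intensity was dropped on [date], and minutes and frequency on [date], [before/after] results by condition were seen.* If minutes and frequency were dropped on Week 1 diaries alone, say so.
4. Optional: descriptive summaries of minutes and frequency by condition and week (for example median and interquartile range), with participants' doubts about these answers noted.

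The cost is one extra model on data already collected, a line or small table of results, and a sentence or two of text. The downside is that readers may take intensity as a second test unless the descriptive label is clear. Any summaries of minutes and frequency would remain hard to interpret.
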